10.7 Safety Analysis

10.7.1 Adverse Events

Adverse Events will be coded using the Medical Dictionary of Regulatory Activities (MedDRA version 23.0), the coded terms will be used for summarizing the AE(s). Only treatment emergent adverse events (TEAE) will be summarized in tables, while all events will be listed. Adverse events will be analyzed using SAF population.

Statistical Analysis Plan
Sponsor: [name], Inc

Study Number: NV-05-983-2020

Version: 2.0 Date: 06JAN2021

An AE will be considered as treatment-emergent if the time of onset is on or after the time of the first study drug administration or any AE that exist prior to first dose and if it increased in severity during the study period. All AEs reported in stage II period- ‘Day of discharge to 59 days after date of first dose of study treatment’ will be considered as TEAE. Handling of missing data and date are explained in section [9.5.1](#) (Imputation of missing data).

An overall summary table, which summarizes, the number and percentages of patients with treatment emergent adverse events at stage I & stage II, serious adverse events, adverse events leading to death, adverse events related to study drug, Study Drug Discontinued Permanently due to adverse event and adverse events by severity categories will be provided by treatment groups.

A separate treatment emergent adverse event table for stage II will be summarized for number and percentage of patients with treatment emergent adverse event (TEAE), serious TEAE, TEAE related to study drug and TEAE by severity categories will be provided by treatment groups.

Patients experiencing any treatment emerging adverse events will be summarized by Preferred Term (PT), SOC and treatment group. The number and percentage of patients with at least one TEAE, SAE, permanently discontinued study treatment (IP) due to AE, AE leading to Death, AE by relationship and TEAEs of severe intensity will be summarized by system organ class, preferred term and treatment group.

Furthermore, listings of SAEs and AEs that lead to study withdrawal will be provided.

AEs Tables by primary system organ class, preferred term and treatment group will be sorted in descending order of counts.

A patient experiencing the same AE multiple times will be counted only once for that preferred term. Similarly, if a patient experiences multiple AEs within the same system organ class that patient will be counted only once in that system organ class. Maximum severity will be considered if a patient has multiple severity reported for same AE. In summaries by relationship, if a subject has the same AE on multiple occasions, the closest relationship to study drug, will be used for summary.

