Indication Under Investigation:	Acute treatment of moderate to severe COVID-19 caused by SARS-CoV-2 infection
Study Objectives:	
Primary Objective:
 
 To evaluate the efficacy of oral favipiravir in improving the time to resolution of hypoxia in moderate to severe COVID-19 patients 
Secondary Objectives
 
 To evaluate the efficacy of oral favipiravir in improving the clinical and virological outcomes in moderate to severe COVID-19 patients To assess the tolerability and safety of favipiravir in the targeted study population
Study Design:	
 Prospective Interventional Randomized (ratio 1:1) Double-blind Placebo-controlled

Study code: NV-05-983-2020
 Protocol No.: CVD-04-CD-001
 Sponsor name: [name], Limited
 Clinical Study Protocol

	
 • As adjunct ('add on') to Supportive Care • Parallel assignment to treatment groups 
This study will be conducted in two parts; Stage I – Main study and Stage II – Extended Follow up. Once all the patients complete the Stage I of the study, the database will be locked, and analysis will be performed. Patients will enter Stage II of study after they complete the Day 28 assessment.

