The study period during which AEs must be reported is defined as the period from the time patient signs the Informed Consent Form to Day 60 or study discontinuation, whichever is earlier. If follow up is required beyond Day 60 for safety related reasons, additional visit(s) may be scheduled for individual patients.

Medical History Condition

Study code: NV-05-983-2020
Protocol No.: CVD-04-CD-001
Sponsor name: [name], Limited
Clinical Study Protocol

A medical history condition is any clinically significant medical/surgical condition already present at the time of informed consent.

Pre-treatment Adverse Events

Any clinically significant abnormality between the time of informed consent and intake of the first dose of the study drug in the trial, which meets the definition of AE, should be recorded as a pre-treatment AE (or non-Treatment Emergent Adverse Event). Any new clinically significant event or worsening of existing medical history condition between the time of informed consent and intake of the first dose of the study drug in the trial, which meets the definition of AE will also be considered as pre-treatment AE.

Treatment Emergent Adverse Events

All AEs recorded after the first dose of study drug (on Day 1) until Day 30 or study discontinuation, whichever is earlier will be considered as Treatment Emergent Adverse Events (TEAEs). Disease signs, symptoms and/or laboratory abnormalities already existing prior to the use of the product will not be considered as adverse experiences after treatment (TEAEs) unless they reoccur after the patient has recovered from the pre-treatment condition or they represent an exacerbation in intensity or frequency, or the character of the condition worsens during the study period.

Post Treatment Adverse Events

All AEs recorded after Day 30 until Day 60 or study discontinuation, whichever is earlier will be considered as post treatment AEs.

Physical Examination Findings

At screening assessment, any clinically significant abnormality detected on physical examination should be recorded as a pre-existing condition. During the visits that fall within the treatment period and after the end of the study, any new clinically significant findings/abnormalities that meet the definition of an AE must be recorded and documented as an AE.

Abnormal Laboratory Values

A clinically significant laboratory abnormality should be documented as an AE if any one of the following conditions is met:

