9.3 Definitions

In the following table, the definitions and calculation of derived variables are summarized

Variable / Term	Definition / Way of calculation
Age	Int ((informed consent date – Birth date +1)/365.25)
Baseline	The last valid value prior to the first dose of study treatment
Treatment Start Date	Date of dose administration on Day 1

Statistical Analysis Plan
Sponsor: [name], Inc

Study Number: NV-05-983-2020

Version: 2.0 Date: 06JAN2021

Variable / Term	Definition / Way of calculation
Treatment End Date	Date of Last Study Medication Taken
Duration of exposure	Treatment end date- Date of randomization + 1
Treatment Emergent AE (TEAE)	An AE will be considered as treatment-emergent if the time of onset is on or after the time of the first study drug administration or any AE that exist prior to first dose and its severity increased during the study.
Time to Resolution of Hypoxia	Date of first time the status trial score to become 4 or lower following baseline assessment when evaluated over a period of 24 hours – Date of randomization +1
Time to discharge	Date of discharge – date of randomization + 1
Time to ALL COVID-19 associated symptoms to become '0=absent' or 'mild =1' from Randomization	Earliest Date of ALL COVID-19 associated symptoms to become either '0=absent' or 'mild =1' in assessments over a period of 24 hours – date of randomization + 1
Time to achieve symptom improvement	Date of Change from baseline value for the particular symptom score to become less than or equal to '-1' and sustained at evaluations over a period of 24 hours – Date of randomization +1
Time to Negative	Date of first time to negative conversion in RT-PCR – Date of randomization + 1

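### SAP 10.7.1 starts the Stage II adverse-event period at discharge and counts every event to Day 60 as treatment-emergent, although Stage II begins after the Day 28 assessment and the protocol ends TEAEs at Day 30

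*SAP*

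**What the plan says.** **Treatment-emergent events.** SAP 9.3 states: "An AE will be considered as treatment-emergent if the time of onset is on or after the time of the first study drug administration". It adds earlier events that worsen and gives no last day. SAP 10.7.1 repeats this and adds a Stage II period, "Day of discharge to 59 days after date of first dose of study treatment", in which all events are TEAEs. Protocol 9.1.1.2 has two categories. "All AEs recorded after the first dose of study drug (on Day 1) until Day 30 or study discontinuation, whichever is earlier" are treatment-emergent; "All AEs recorded after Day 30 until Day 60 or study discontinuation" are post-treatment.

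**Stage boundary.** Protocol synopsis, Study Design: "Patients will enter Stage II of study after they complete the Day 28 assessment". Protocol 3.1.1 and SAP 8.1.1 both complete Stage I with the Day 28 assessment, by telephone if the patient has already gone home. Protocol 3.1.5 caps Stage II at 34 days.

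**Tables.** SAP 10.7.1: "Only treatment emergent adverse events (TEAE) will be summarized in tables"; other events are only listed. An overall summary shows TEAEs for each stage, and in addition "A separate treatment emergent adverse event table for stage II will be summarized", by treatment group. SAP section 12 plans one database lock per stage.

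**Related text.** Protocol 3.1.3.2.2 makes TEAEs the Stage II safety endpoint, and Protocol 6.3.2.1 and 6.3.2.2 collect them on Days 42 and 60. SAP section 11, on deviations from the protocol, says that none apply.

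**The concern.** There are two separate conflicts. One is the last day of a treatment-emergent event: Day 30 in the protocol definition, Day 60 in the SAP. The other is the first day of Stage II: after the Day 28 assessment in both design descriptions, the day of discharge in the SAP's adverse-event rule.

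Both affect the content of the safety tables. Only TEAEs are tabulated, so the end day decides whether an event in the second month appears in a table or only in a listing. The start day decides which stage an event belongs to. A Stage II table should describe extended follow-up. Under the discharge rule it also takes in Stage I events and, for patients who go home before Day 10 and continue study drug there, events during dosing.

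The start is also a post-randomisation event judged by the investigator, and SAP 10.6.2 compares time to discharge between arms as the first secondary endpoint. A percentage with at least one event, taken over a window that opens at such an event, mixes event rate with length of observation.

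**Working it through.** **1. The plan's own durations.** Inputs from Protocol 3.1.5: screening up to 3 days, data collection 28 (+2) days, telephone follow-up on Day 60 (+2).
- Stage I: 3 + 28 + 2 = 33 days, as stated.
- Stage II: 60 + 2 − 28 = 34 days, as stated.
- Total: 33 + 34 = 67 days, as stated.

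The 34-day figure therefore rests on a Day 28 start.

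**2. The window in SAP 10.7.1.** With first dose on Day 1, 59 days later is Day 60. For discharge on Day D, counting both end days:
- Stage II window = 60 − D + 1 = 61 − D days
- days also in Stage I = 28 − D + 1 = 29 − D days

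| Discharge day | SAP Stage II window (days) | Days also in Stage I |
|---|---|---|
| 5 | 56 | 24 |
| 8 | 53 | 21 |
| 10 | 51 | 19 |
| 14 | 47 | 15 |
| 21 | 40 | 8 |
| 28 | 33 | 1 |

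Every row except the last exceeds 34 days.

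**3. Patients at the extremes.** Dosing runs to Day 10. A patient discharged on Day 8 has Days 8 to 10, 10 − 8 + 1 = 3 dosing days, inside the Stage II window. A patient still in hospital after Day 28 has finished Stage I but has no Stage II window until discharge. A patient who dies in hospital never has one.

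**4. The TEAE end day.** Day 60 rather than Day 30 adds 60 − 30 = 30 days, and reaches 60 − 10 = 50 days past the last dose. With Stage II fixed at Days 29 to 60, every patient followed to Day 60 has 32 days. Under the protocol definition only Days 29 and 30 of these are treatment-emergent, and the other 30 are post-treatment.

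**5. Possible size of an arm difference (illustration only).** Assumptions not in the documents: exponential discharge times; control probability p of discharge by Day 28 of 0.7, 0.8 or 0.9; a window starting at Day 28 for patients not discharged by then; the same constant event rate in both arms, 0.01 or 0.02 per day. The discharge hazard ratio is set to 1.25, borrowed from the sample-size section, where it refers to clinical improvement.

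With λ = −ln(1 − p)/28 and hazard ratio h, the mean time to the earlier of discharge and Day 28 is r(h) = (1 − exp(−28λh))/(λh). The mean window is 60 − r(h). At p = 0.8, λ = 0.0575 and the mean window is 46.1 days on control and 47.9 on favipiravir.

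| Control p | Mean window, control / favipiravir (days) | At least one event, rate 0.01 | At least one event, rate 0.02 |
|---|---|---|---|
| 0.7 | 43.7 / 45.5 | 35.1% / 36.3% | 57.4% / 59.0% |
| 0.8 | 46.1 / 47.9 | 36.6% / 37.8% | 59.4% / 61.0% |
| 0.9 | 49.1 / 50.8 | 38.5% / 39.6% | 61.9% / 63.3% |

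The window is about 1.8 days longer on average on favipiravir, and the percentage is 1.1 to 1.6 points higher from window length alone. With a hazard ratio of 1 both differences are zero. A fixed 32-day window gives 27.4% or 47.3% in both arms.

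**The case against.** - **Precedence.** The protocol lets the SAP prevail where planned analyses differ, and Protocol 1.5.3 allows analysis changes to be documented in the SAP. This stands for the TEAE end day: Day 60 is the operative rule, though undeclared. It does not settle the stage boundary, because SAP 8.1.1 and SAP 10.7.1 disagree with each other.
- **Day 60 agrees with part of the protocol.** TEAEs are the protocol's Stage II endpoint and are collected on Days 42 and 60. This stands, and it rules out treating the protocol as right and the SAP as the sole departure. Adopting Day 30 alone would leave two days of Stage II for that endpoint, or none if the Day 28 assessment falls on Day 30 within its +2-day window.
- **A discharge start has a purpose elsewhere.** The Stage II relapse endpoint also runs from discharge to Day 60, and relapse there is defined from the day of discharge. Adverse events are recorded for every patient from consent, so that reason does not carry over.
- **The overlap is inferred.** The SAP states no Stage I adverse-event window; the overlap follows from where SAP 8.1.1 ends Stage I. It concerns stage-specific rows only, and only patients discharged before Day 28. Within a table each patient counts once per preferred term and system organ class. That rule does not assign an event to one stage.
- **The tables are descriptive.** No between-arm test of adverse events is planned. Drug-related, serious and severe events are also shown separately, and all events are listed. This limits the consequence: no formal inference is biased, and any dilution by late background events has not been quantified.

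**Conclusion.** The two definitions conflict, and the discharge-based Stage II period cannot be reconciled with the SAP's own account of where Stage I ends. The certain part is textual and arithmetical: 29 − D days assigned to two stages for a patient discharged on Day D before Day 28, Stage II windows well above the stated 34 days for most discharge days, and a TEAE period 30 days longer than the protocol defines, with no deviation declared.

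Two stronger readings are tempting. A reader might infer that the SAP observes the arms over different windows, or that earlier discharge in one arm lengthens the window equally for each of its patients. The documents do not support either. The window follows the individual patient's discharge. It differs between arms only on average, and only if treatment changes time to discharge; the 1.1 to 1.6 points above rest entirely on the stated assumptions. A reader might also infer that all the TEAE tables are compromised. They are not: the all-study TEAE window does not depend on discharge.

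What remains is a fault in the stage-specific safety summaries and an unresolved TEAE end day in both documents. It should be corrected before the Stage I lock. The primary efficacy analysis is not affected.

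**What to change.** 1. In SAP 10.7.1, replace the discharge-based period with stage windows fixed by study day for all patients, whether or not discharged: Stage I from first dose to the Day 28 assessment, Stage II after it to Day 60. State how the +2-day window is treated at the boundary.
2. Assign each adverse event to one stage by its onset date.
3. State one TEAE end day in SAP 9.3, SAP 10.7.1 and Protocol 9.1.1.2.
4. If Day 30 is kept, add a post-treatment table by arm for Days 31 to 60, so that these events are not reduced to listings, and reword the Stage II safety endpoint (Protocol 3.1.3.2.2, SAP 8.3) and the Day 42 and Day 60 collection items to match. If Day 60 is chosen, revise the protocol's post-treatment category.
5. Record the change in SAP section 11.

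The cost is SAP wording, table shells and a small alignment of protocol wording. Adverse events are already collected to Day 60, so no new data are needed.

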10.7.2 Laboratory assessments

Laboratory assessments will be measured at screening, Day 4, Day 7, Day 10, Day 14, Day 21 and Day 28 or discharge (if discharge happens earlier than one or more of the above-mentioned timepoints). Laboratory assessments will be summarized by treatment group and time point using SAF population.

The actual and change from baseline laboratory assessments parameters will be summarized descriptively by time point and treatment group.

Statistical Analysis Plan
Sponsor: [name], Inc

Study Number: NV-05-983-2020

Version: 2.0 Date: 06JAN2021

The results falling out of normal ranges will be classified as High and Low and will be summarized by time point and treatment group. In addition, number and percentage of patients having 'Normal', 'Abnormal CS' and 'Abnormal NCS' results for laboratory parameters will be summarized by visits and treatment group.

Data listings will be presented for laboratory parameters.

10.7.3 Vital Signs

Vital signs will be measured at Screening, Day 1, Day 2 to Day 28 or discharge (if discharge happens earlier)

Vital signs will be analyzed using SAF population.

The vital signs parameters include:

- Systolic Blood Pressure (mmHg)
- Diastolic Blood Pressure (mmHg)
- Heart Rate (bpm)
- Respiratory Rate (brpm)
- Body Temperature (°F)
- Blood Oxygen Saturation (SpO2) (%)

The actual and change from baseline vital signs parameters will be summarized descriptively by visits and treatment group.

Data listings will be presented for vital signs parameters.

10.7.4 ECG

ECG will be assessed at Screening, Day 1, Day 4, Day 7, Day 10, Day 14, Day 21 and Day 28 or discharge (if discharge happens earlier then one or more of the above-mentioned timepoints). The ECG parameters are as follows:

- PR Interval
- RR Interval
- QRS Duration
- QT Interval
- QT_cB Interval
- Heart Rate

The actual and change from baseline of quantitative ECG parameters will be summarized descriptively by visits and treatment group.

Statistical Analysis Plan
Sponsor: [name], Inc

Study Number: NV-05-983-2020

Version: 2.0 Date: 06JAN2021

Quantitative ECG parameters will be analyzed descriptively and the proportion of patients in each class based on ECG interpretation (Normal, Abnormal CS, Abnormal NCS) will be summarized by frequencies and percentages using the SAF population by time point and treatment group.

Listing will be provided for the ECG.

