	
 ▪ 12-lead ECG: Changes in heart rate, PR, QRS, QT and QTcB intervals. 
Stage II
 
Efficacy endpoint:
 
 1. Percentage of patients reporting a clinical relapse of COVID-19 when assessed from day of discharge to 59 days after the day of randomization (Day 60). 
Note: 'Clinical relapse' is defined as either the reappearance or worsening of severity (over the assessment on the day of discharge) of one or more of the above-mentioned COVID-19 associated symptoms, or the appearance of any of these symptoms (due to COVID-19 infection) for the first time after discharge.
 
 2. Proportion of patients 
 a. With disease worsening and requires: 
 • Admission to ICU • High flow nasal oxygen • Non-invasive mechanical ventilation • Invasive mechanical ventilation 
AND
 
 b. Dying 
until Day 60 (regardless of whether patients are discharged from hospital before Day 28 or not)
 
Safety Endpoint:
 
 1. Number (and percentage) of patients reporting treatment emergent adverse events (TEAEs) (by MedDRA system organ class and preferred term) 
Secondary endpoints may be modified, or additional secondary endpoints may be defined in the SAP.

Statistical Analyses:
	
Unless otherwise specified, the primary efficacy analysis will be done using Intention to Treat (ITT) population. The statistical significance level is 0.05 by one sided or two-sided test, wherever appropriate. Mean/ Median (and other general statistics estimates such as Inter Quartile range, SD, min, max etc.) and the 95% CI for the estimates of the mean will be provided for the applicable efficacy endpoints.

Study code: NV-05-983-2020
Protocol No.: CVD-04-CD-001
Sponsor name: [name], Limited
Clinical Study Protocol

Endpoints will be analysed descriptively and inferentially wherever necessary.

All AEs and TEAEs will be summarized in terms of severity, relationship to study treatment, action taken and patient outcome. The number and the proportion of patients who experienced AEs will be computed by treatment group, classified by Medical Dictionary for Regulatory Activities (MedDRA version 23.0) Primary System Organ Class and Preferred Terms. The AE data will be summarized using safety population.

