4.1.1 Inclusion Criteria

Patients must satisfy all the following criteria to be included in the study:

1. Male and female patients aged 21 to 80 years (both inclusive)
2. Patients who have tested positive for SARS-CoV-2 by RT-PCR assay using a respiratory tract sample (either nasopharyngeal swab OR oropharyngeal swab OR nasal aspirate OR tracheobronchial aspirate) collected within 72 hours prior to randomization
3. Patients should be hospitalized
4. Patients having moderate or severe COVID-19* with a score of > 4 on the 10-point ordinal scale of clinical status used by WHO in the SOLIDARITY trial, at baseline assessment [i.e., patients with blood oxygen saturation (SpO₂) <95% at rest on room air at sea level and requiring supplemental oxygen].

*Note: This includes patients clinically assigned as:

- I. 'moderate' COVID-19
 - a. symptoms which could include fever, cough, sore throat, malaise, headache, muscle pain, gastrointestinal symptoms or shortness of breath with exertion and/or clinical signs, such as respiratory rate ≥ 20 breaths per minute or heart rate ≥ 90 beats per minute
 - AND
 - b. blood oxygen saturation (SpO₂) of 94% at rest on room air at sea level
- II. 'severe' COVID-19
 - a. symptoms which could include any symptom of moderate illness or shortness of breath at rest, or respiratory distress and/or clinical signs, such as respiratory rate ≥ 30 per minute or heart rate ≥ 125 per minute
 - AND
 - b. blood oxygen saturation (SpO₂) $\leq 93\%$ on room air at sea level or PaO₂/FiO₂ <300*

Study code: NV-05-983-2020
 Protocol No.: CVD-04-CD-001
 Sponsor name: [name], Limited
 Clinical Study Protocol

The above-mentioned definitions of COVID-19 severity are adapted from the FDA Guidance document COVID-19: Developing Drugs and Biological Products for Treatment or Prevention - Guidance for Industry Final Document dated May 2020²⁴

5. Female patients of childbearing potential*

- a. must have a negative serum pregnancy test at screening
- b. should not be lactating; and not planning to become pregnant/breast feed during the treatment period and for 7 days after the last dose of study medication.
- c. should commit to the use of **TWO** forms of study-acceptable contraception methods, including a barrier method (eg. diaphragm) along with one or more of the following methods of contraception for the duration of the treatment period and for 7 days after the last dose of study medication:

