7.2 Safety Evaluation Criteria

7.2.1 Stage I

1. Number (and percentage) of patients reporting treatment emergent adverse events (TEAEs) (by MedDRA system organ class and preferred term)

The AEs and SAEs occurring throughout the study will be collected irrespective of whether they are related to investigational product or not and will be presented as per the System Organ Class (SOC). The number of patients with treatment-emergent AEs will be collected and summarized based on the SOC and preferred term.

2. Changes of parameters at each assessment during the study/follow-up period, compared to baseline for:
 - Vital signs: body temperature, heart rate, respiratory rate, systolic/diastolic BP and oxygen saturation.
 - Clinical laboratory assessments: hematology, serum chemistry, urinalysis.
 - 12 Lead ECG: Changes in heart rate, PR, QRS, QT and QTcB intervals.

Vital signs will be measured at screening, at pre-dose only on Day 1 and at least twice, morning and afternoon, daily from Day 2 to Day 28 or discharge or discontinuation from the study. Laboratory assessments will be performed at screening, Day 4, Day 7, Day 10, Day 14, Day 21, and Day 28 or discharge or discontinuation. 12-Lead ECG will be performed at screening, Day 1

Study code: NV-05-983-2020
Protocol No.: CVD-04-CD-001
Sponsor name: [name], Limited
Clinical Study Protocol

(pre-dose), Day 4, Day 7, Day 10, Day 14, Day 21 and Day 28 or discharge (if discharge happens earlier than one or more of the above-mentioned assessment timepoints or study discontinuation (whichever is earlier). Pre-dose measurement will act as the baseline for vital signs, laboratory assessments and 12-Lead ECG parameters. The changes in these parameters will be compared between the treatment groups for each of these assessments.

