9.7 Electrocardiograms

12-lead electrocardiogram (ECG) will be recorded with the patient at rest in the supine position at screening, once daily (preferably at the same time on each day) on Day 1, Day 4, Day 7, Day 10, Day 14, Day 21 and Day 28 or discharge (if discharge happens earlier than one or more of the above-mentioned assessment timepoints) or Study Discontinuation, whichever is earlier, and heart rate (HR), RR, PR, QRS, QT and QTcB intervals, and the presence or absence of clinically significant abnormalities will be recorded. Changes in ECG parameters will be recorded as AEs if the Investigator judges these as being clinically significant.

Study code: NV-05-983-2020
Protocol No.: CVD-04-CD-001
Sponsor name: [name], Limited
Clinical Study Protocol

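### QTcB is the only rate-corrected QT planned, so within-arm change from an acute-illness baseline is pulled down as heart rate recovers, while the between-arm difference is largely preserved

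*SAP*

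**What the plan says.** The ECG safety endpoint in the protocol synopsis is "12-lead ECG: Changes in heart rate, PR, QRS, QT and QTcB intervals", measured against baseline. Protocol 7.2.1 repeats it, makes the pre-dose ECG the baseline, and says changes will be compared between the treatment groups at each assessment. SAP 9.3 likewise defines baseline as the last valid value before the first dose.

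Protocol 9.7 lists what is captured: "RR, PR, QRS, QT and QTcB intervals, and the presence or absence of clinically significant abnormalities will be recorded". SAP 10.7.4 analyses the same parameters, and "QT_cB Interval" is the only rate-corrected QT among them. The analysis is: "The actual and change from baseline of quantitative ECG parameters will be summarized descriptively by visits and treatment group". In addition, "the proportion of patients in each class based on ECG interpretation (Normal, Abnormal CS, Abnormal NCS) will be summarized by frequencies and percentages", and an ECG listing is provided. Neither document plans a second correction formula or a heart-rate adjustment.

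On heart rate at entry, Protocol 4.1.1 gives a rate of at least 90 as an example sign of moderate disease. For severe disease the example signs are "respiratory rate ≥ 30 per minute or heart rate ≥ 125 per minute". The required element in both definitions is oxygenation.

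**The concern.** Bazett's formula divides QT by the square root of RR. If the true dependence of QT on RR is weaker than a square root, QTcB reads too high at fast rates, and the excess shrinks as the rate slows. Baseline here is taken in hospitalised, hypoxic patients. The sample-size section expects resolution in 0.9 of the test group and 0.8 of the control group, so most patients should recover on study. Where heart rate settles with recovery, change in QTcB mixes any drug effect with that settling, and the two can have opposite signs.

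At stake is how a named safety endpoint of a phase III trial is read: a per-arm table could show QTcB falling on favipiravir while the heart-rate-independent QT had lengthened.

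**Working it through.** The documents state no QT figure (no threshold, margin or SD), so there is no plan figure to reproduce. The check asks how far QTcB moves when heart rate falls.

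**Inputs from the documents.** Heart rates of 90 and 125 bpm (example signs, Protocol 4.1.1); QT and RR recorded at each ECG (Protocol 9.7); design hazard ratio 1.25 and event probabilities 0.9 and 0.8 (SAP 9.6).

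**Assumptions, not in the documents.** QT = QTc × RR^b with b = 1/3 (base case), 0.40 or 0.50; QTc 390 to 410 ms; recovered heart rate 75 bpm.

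**Formulas.** RR = 60/HR; QTcB = QT/RR^(1/2); QTcF = QT/RR^(1/3). Hence QTcB = QTc × (HR/60)^(1/2 − b).

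**1. Within-arm shift with no true change** (b = 1/3, QTc 390 ms)

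- 125 bpm: 390 × (125/60)^(1/6) = 390 × 1.1301 = 441 ms
- 90 bpm: 390 × 1.0699 = 417 ms
- 75 bpm: 390 × 1.0379 = 405 ms

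The shift is -12.5 ms from 90 to 75 bpm and -36 ms from 125 to 75 bpm. With QTc 410 ms the figures are -13.1 and -37.8 ms. QTcF shifts by 0 in this base case.

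**2. Largest true rise that still reads as a fall**: QTc × [(HR0/HR1)^(1/2 − b) − 1], with QTc 410 ms

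| HR fall | b = 1/3 | b = 0.40 | b = 0.50 |
|---|---|---|---|
| 90 to 75 | 12.6 ms | 7.5 ms | 0 |
| 100 to 75 | 20.1 ms | 12.0 ms | 0 |
| 125 to 75 | 36.4 ms | 21.5 ms | 0 |

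Illustration for one patient: QT 300 ms at 125 bpm, then 370 ms at 75 bpm. QTcB goes from 433.0 to 413.7 (-19.3 ms). QTcF goes from 383.2 to 398.6 (+15.4 ms).

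**3. Uncorrected QT errs the other way.** At QTc 410 ms and b = 1/3, slowing from 100 to 75 bpm lengthens QT from 345.8 to 380.6 ms (+34.8 ms) with no true change.

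**4. Between-arm difference in change.** Assume equal baselines, placebo settling at 75 bpm and favipiravir at 75 − x. For a true effect d, the difference is (QTc + d) × ((75 − x)/60)^(1/2 − b) − QTc × (75/60)^(1/2 − b). With QTc 410 ms and b = 1/3:

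| Extra HR fall x | d = 0 | d = +5 ms | d = +10 ms |
|---|---|---|---|
| 0 bpm | 0.0 | +5.2 | +10.4 |
| 1 bpm | -1.0 | +4.2 | +9.4 |
| 5 bpm | -4.9 | +0.3 | +5.4 |

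At b = 0.40 and x = 5, the d = 0 entry is -2.9 and the d = +10 entry is +7.3.

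**5. What x is plausible under the trial's own effect size.** Suppose heart rate settles when hypoxia resolves (an assumption) and every patient contributes an ECG at the time compared. If s is the control proportion unresolved, the gap under hazard ratio 1.25 is s − s^1.25. This is largest at s = 0.8^4 = 0.41: 0.4096 − 0.3277 = 0.082. The 0.9 and 0.8 event probabilities give 0.10. The mean extra fall is then:

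- 0.082 to 0.10 × 15 bpm = 1.2 to 1.5 bpm if all start at 90 bpm
- 0.082 to 0.10 × 50 bpm = 4.1 to 5.0 bpm if all start at 125 bpm

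Table 4 turns this into a bias of roughly 1 to 5 ms.

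**The case against.** The strongest reply is that the trial has a concurrent randomised placebo arm. Summaries are by treatment group, Protocol 7.2.1 promises a comparison, and heart-rate recovery common to both arms cancels: a true +10 ms reads as +10.4 ms. This stands. A reader might infer that the plan would give the wrong sign for the arm difference. The documents do not support that: under the design's own effect size the bias is a few milliseconds, so only a true effect of that order could be cancelled or reversed.

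A reader might also infer that the trial enrols febrile, tachycardic patients. It need not. Fever and heart rate are example features, and no baseline heart-rate distribution is given, so the -36 ms case describes a patient starting at 125 bpm, not the cohort.

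A third tempting reading is that QTcB is the only evidence on QT safety. It is not: uncorrected QT, RR and heart rate are summarised too, ECGs are classed by clinical significance, significant changes are recorded as AEs, and listings are given. But raw QT moves the opposite way as heart rate falls, and the class, AEs and listings describe individual patients. None supplies a corrected QT free of the heart-rate shift.

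Two further points stand. QTcF is not assumption-free: its residual exponent is b − 1/3 against 1/2 − b for Bazett, so the two err equally at b = 5/12 (about 0.42) and QTcF is better only below that. At b = 0.40 and QTc 410 ms, a fall from 90 to 75 bpm moves QTcF by +4.9 ms and QTcB by -7.7 ms. Also, no eligibility, discontinuation or interim rule in the documents uses QTc, and Protocol 1.3 does not list QT prolongation among the known risks.

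**Conclusion.** The point holds for within-arm change. With QTcB as the sole corrected QT and a baseline in acute illness, patients whose heart rate settles from 90 to 75 bpm show a spurious fall of about 12 to 13 ms, and from 125 to 75 bpm one of about 36 to 38 ms, if b is 1/3. The shift is smaller at b = 0.40 and absent at b = 0.50. A true prolongation of similar size can read as no change or a fall.

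The between-arm difference is largely preserved when heart rate recovers equally. It leans toward hiding prolongation only to the extent that heart rate falls more on favipiravir. Since SAP 10.7.4 specifies per-arm descriptive summaries and no between-arm estimate, the more distorted quantity is the one the plan puts in front of the reader.

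The sizes rest on an assumed exponent, QTc and recovery heart rate; the documents fix none of them. The consequence is confined to descriptive safety reporting. The primary endpoint, sample size and type I error are untouched. The change is worth making because it is nearly free.

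**What to change.** In SAP 10.7.4:

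- Derive QTcF = QT/RR^(1/3) (RR in seconds) from the QT and RR already recorded.
- Make change from baseline in QTcF, by visit and arm, the main corrected-QT summary. Keep QTcB beside it as supportive, so that dependence on the correction formula is visible.
- Present the between-arm difference in change with a 95% CI at each visit, which delivers the comparison Protocol 7.2.1 promises and uses the placebo arm to remove shared heart-rate recovery.

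The cost is one derived variable and one extra table. No procedure, visit or data collection changes.
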